Animal and laboratory data exist to support the theory of angiogenesis imbalance as the root cause of preeclampsia. Overexpression of sFlt-1 induces hypertension and fetal growth restriction in pregnant mice, and the time course of blood pressure increase mirrors the increase in sFlt-1.²² The preeclampsia-like clinical phenotype associated with sFlt-1 expression occurs via activation of the endothelin (ET) system.^{23, 24} In humans, low plasma vascular endothelial growth factor (VEGF) in the first trimester of pregnancy is a predictive marker for preeclampsia. In addition, sFlt-1/PlGF ratios are increased in women who subsequently develop preeclampsia compared to normotensive women.²⁵ ~90% of women with EOP have elevated sFlt-1.²⁶ An sFlt-1/PlGF ratio >0.85 is associated with adverse pregnancy outcomes: placental abruption, elevated liver enzymes and/or low platelets, and small-for-gestational-age birth weight and/or absent/reversed umbilical artery Doppler, and significantly shorter latency period, among women with EOP. 75% of women with sFlt-1/PlGF >0.85 deliver within one week and 85% within two weeks, compared to only 10% and 15% of women with sFlt-1/PlGF <0.85. sFlt-1/PlGF is a useful discriminator for women with EOP who are at risk for adverse outcome and need for delivery prior to 34 weeks.²⁷ The natural history of circulating sFlt-1 levels among women with preeclampsia has been described in several longitudinal studies.^{28, 29} sFlt-1 levels are elevated prior to the development of clinical symptoms of preeclampsia, and remain elevated until delivery.¹⁷ Based on this data, we believe that elevated circulating sFlt-1 levels identify those women at greatest risk for adverse outcome, particularly if managed expectantly, and thus the women most likely to yield benefit from treatments that allow for longer latency.

To address the angiogenic imbalance believed to be in the pathophysiology of preeclampsia, we²⁴ and others³⁰⁻³³ have demonstrated that ET receptor antagonists greatly ameliorate the preeclampsia-like phenotypes induced by sFlt-1 in animal models. While this data is promising, ET receptor antagonists are teratogenic and contraindicated in pregnant

[figure not shown]
[figure not shown]

Figure 1. Percent of medically indicated preterm birth (PTB) due to preeclampsia (PEX), fetal distress, small for gestational age (SGA), and abruption

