3.1 General Design

This is an open labeled phase II study of vitamin B₃-amide dietary supplementation in pregnant women with early-onset preeclampsia, per ACOG guidelines. We will enroll 24 pregnant women at 24-33 weeks 3 days with EOP and anticipated treatment by expectant observation. If the woman is anticipated to remain undelivered for 48 hours after diagnosis she will receive vitamin B₃-amide, 2.5 mg/day dosed in the following manner: administered as 1000mg at 8AM and 12MN; 500mg at 4PM, continuing until delivery or 34 weeks, whichever occurs first. Optional research blood samples will be collected at times of clinically indicated blood draws (baseline and 2-3 times per week) to measure nicotinamide and its metabolite 2-pyridone, sFlt-1 and PIGF. A sample of cord blood will be collected (6ml) following delivery.

All study subjects will receive standard surveillance and treatment for expectant management of EOP, which may include but is not limited to:

- Daily prenatal vitamin
- 24-hr urine collection for protein excretion at admission
- Blood sampling for hematologic, liver, and kidney function at time of diagnosis and every 2-3 days thereafter
- Magnesium sulfate for seizure prophylaxis
- Betamethasone to accelerate fetal lung maturity
- Antihypertensive agents
- Twice weekly fetal surveillance by NST (30 minutes of continuous fetal heart rate monitoring) or BPP (30 minutes of ultrasound to monitor for fetal breathing, movement, fluid)
- Weekly ultrasound to measure amniotic fluid and UA Dopplers

In addition to above standard care for EOP, subjects will receive surveillance and treatment solely for study purposes, including:

- Daily administration of vitamin B₃-amide, 2.5 Gm/day in 3 divided doses; "on treatment" is defined as within 24 hours of dose
- Daily (M-F) study staff visit to query side effects if in-patient; with each outpatient visit (typically twice a week) if discharged from the hospital
- Optional blood sampling to coincide with clinical blood draws to measure sFlt-1, nicotinamide and 2-pyridone levels; chart abstraction to review liver function testing results (done clinically)
- Chart abstraction for maternal and delivery data (up until maternal discharge) and neonatal data (until 30 days of age or until discharge, whichever occurs first). We will

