4.4 Early Withdrawal of Subjects

4.4.1 When and How to Withdraw Subjects

Subjects may withdraw at any time and for any reason. Subjects may be withdrawn if they no longer meet eligibility criteria; or if in the opinion of the investigator it is not in the subject's best interest to continue. A subject may also be withdrawn if she experiences an unmanageable or irreversible adverse Grade 3 or 4 adverse event using the CTCA v3.0 criteria as defined in section on safety monitoring. The date of withdrawal from study participation will be recorded in the CRF. Subjects who either complete or are removed from the treatment phase at any time will have complete data chart abstracted and recorded for study purposes.

Specific study stopping rules include:

- Any maternal or fetal death deemed to be related or possibly related to study participation
- More than expected prevalence of liver toxicity within 24 hours of study drug, thus > 20% of subjects experience liver toxicity (more than 1 subject for every 5 subjects enrolled)
- More than expected prevalence of fetal side effects (defined as BPP < 6 OR UA Dopplers show absence or reversal of diastolic blood flow), (more than 1 delivery for fetal reasons per every 5 subjects enrolled)

Specific rules to stop study intervention for individual subject

- Delivery, or two weeks of treatment (“on-treatment” defined as within 24 hours of study drug)
- Liver toxicity (LFTs \geq 3x ULN within 24 hours of study drug)
- Maternal side effects that cannot be managed with oral medication

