4.4.2 Data Collection and Follow-up for Withdrawn Subjects

Withdrawn subjects will have data collected through delivery events. The full data set will include subjects who enroll and receive at least 72 hours of vitamin B₃A dietary supplementation, as the primary outcome will be measured at 72 hours. Every effort will be made to obtain data on all enrolled subjects, even if they are withdrawn and deliver elsewhere.

5 Study Agent

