5.2 Treatment Regimen

Subjects will receive vitamin B₃-amide dietary supplementation, 2.5Gm/day daily until delivery or 34 weeks' gestation whichever occurs first. “On-treatment” is defined as 24 hours of study drug.

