5.3 Preparation and Administration of Study Agent

Major Pharmaceuticals will supply the vitamin B₃-amide (study agent). The study agent will be stored by either the UNC or the WakeMed pharmacy and dispensed via pharmacy services following enrollment.

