- Blood sampling at baseline (pre-dose), 2 hours post dose, 8 hours post dose and 24 hours post dose.
- Urine sample at baseline (pre-dose), 8 hours post dose and 24 hours post dose.
- This will be done either in the clinic or the CTRC

6.3 **Laboratory specimen handling procedures**

Blood for research purposes will be collected at the time of clinically indicated blood draws. Specimens will be labeled with the subject's unique study ID and processed.

Specimens to be tested for circulating sFlt-1 and PlGF levels will be stored and shipped as a single batch on dry ice to the research laboratory at Harvard University. The interassay coefficient of variance for sFlt1 and PlGF immunoassays ranges from 2.6% to 3.0%.

Specimens collected for nicotinamide and 2-pyridone measurements will be sent to the UNC School of Pharmacy Lab ([name]). [name] developed a LC-MS/MS method using protein precipitation (acetonitrile) to measure nicotinamide and 2-pyridone during our previous phase I study.

7 **Statistical Plan**

7.1 **Statistical Methods**

Sample size: The study sample size was calculated to the primary outcome of MAP. We stipulated *a priori* that $\alpha = .05$ and $\beta = 0.2$. Using the highest BP measured within each 24-hr period and applying the following formula we will calculate daily MAP:

$$\text{mean arterial BP} = [2(\text{diastolic BP}) + \text{systolic BP}] \div 3$$

Assuming that the mean (\pm sd) MAP at enrollment of our subjects is 107 (\pm 10) mm Hg, to detect a difference from enrollment to 48 hours after treatment of 7 mm Hg in MAP requires that 20 subjects be enrolled. We will enroll 24 to allow for 20% attrition due to delivery prior to 48 hours of treatment.

- We will use a repeated measurement ANOVA to compare baseline MAP to MAP at 48 hours, 7 days and weekly thereafter until delivery or 34 weeks.
- Maternal liver toxicity: the proportion of women who develop elevated liver function tests (ALT and/or AST \geq 3x ULN within 24 hours of study drug) will be determined and compared to expected proportion of 20%.
- Descriptive report of proportion of women with
 - Side effects
 - Fetal effects

7.2 **Subject Population(s) for Analysis**

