All subjects will be included in the analysis, regardless of whether they received investigational agent. Subject demographic and baseline characteristics will be summarized. Descriptive summaries will include the number of subjects, mean, standard deviation, median, minimum and maximum for continuous parameters, frequency and percentages for categorical parameters.

8 Safety and Adverse Events

The PI and/or study staff will conduct daily medical monitoring for unanticipated problems, AEs, and serious AEs and record and report them to the UNC or WakeMed (respectively-dependent on where they are cared for) IRB and FDA as outlined below (Sections 8.2, 8.3, 8.5). The FDA will be notified after 1 case of liver toxicity and after every 1 case of delivery within 48 hours of enrollment, and will conduct ad-hoc review as they deem appropriate.

Study stopping rules and subject withdrawal for safety reasons are described previously (Section 4.4) and below (Section 8.4).

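### The liver-toxicity proportion has two conflicting denominators, and neither suits a safety rate: one keeps women never dosed, the other drops women with under 72 hours of drug

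*Combined protocol and SAP*

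**What the plan says.** **Population.** Section 7.2 states: "All subjects will be included in the analysis, regardless of whether they received investigational agent". Neither 7.1 nor 7.2 names a separate safety population.

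**A second population.** Section 4.4.2 reads: "The full data set will include subjects who enroll and receive at least 72 hours of" the supplement. The reason given there is the timing of the primary outcome.

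**Endpoint.** Sections 3.2 and 7.1 count liver toxicity as ALT and/or AST at or above three times the upper limit of normal within 24 hours of study drug. Section 3.1 adds that on-treatment status "is defined as within 24 hours of dose".

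**Comparison.** Under 7.1 the proportion "will be determined and compared to expected proportion of 20" percent. No denominator, time period or test is given. Side effects are reported as a proportion of women, also without a stated denominator.

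**Stopping rule.** Section 4.4.1 applies when more than "20% of subjects experience liver toxicity (more than 1 subject for every 5 subjects enrolled". Section 8.4 repeats the 20% without the reference to enrolment.

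**Exposure.** Drug is "dispensed via pharmacy services following enrollment" (5.3), so a woman can be enrolled and not dosed. Section 5.2 plans "2.5Gm/day daily until delivery or 34 weeks", and 8.4 agrees, but 4.4.1 ends individual treatment at delivery or two weeks. Liver tests are clinical draws, every 2-3 days in 3.1 and 6.2 but every 2-7 days in 5.5.

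**The concern.** Safety is the second objective in the Study Summary, and the liver proportion is its main measure. The numerator is limited to time on drug, while the denominator in 7.2 is not limited to women who had any drug. That mismatch works in one direction only: each undosed woman lowers the rate. The 72-hour set in 4.4.2 removes the undosed women but also removes women with one or two days of drug, together with any toxicity they had. That bias can go either way.

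A dosed woman who delivers before any post-dose liver test is a related problem. She has no measured outcome, and the plan does not say whether she counts as toxicity-free.

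What is at stake is whether the figure set against 20% can be interpreted. Two analysts following two sections of the same document could report different percentages from the same data.

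**Working it through.** **1. Where the denominator comes from.** The plan has no size or power calculation for liver toxicity. The number of women comes from the blood-pressure calculation in 7.1: change of 7 mm Hg, SD 10, α = 0.05, power 80%. A two-sided paired t-test gives n = 19 if the SD of the change is taken as 10 (an assumption, since the plan gives only the SD at enrolment). Power at n = 20 is 84.4%. This is close to the stated 20. The text then enrols 20 × 1.2 = 24. The Study Summary has 25, which equals 20 ÷ 0.8.

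**2. Never-dosed women, 7.2 denominator.** With k of 24 never dosed and true risk p among dosed women, the reported proportion is on average p × (24 − k)/24. The documents do not give k; 0 to 5 is assumed. Exceeding 20% of n requires the smallest whole number above 0.2n.

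| k never dosed | 0 | 1 | 2 | 3 | 4 | 5 |
|---|---|---|---|---|---|---|
| True 20% shows as | 20.0% | 19.2% | 18.3% | 17.5% | 16.7% | 15.8% |
| Cases to exceed 20% of 24 | 5 | 5 | 5 | 5 | 5 | 5 |
| Cases to exceed 20% of dosed women | 5 | 5 | 5 | 5 | 5 | 4 |

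The count changes only at k = 5 (0.2 × 19 = 3.8, so 4 cases). There, with a true risk of 30%, the binomial chance of crossing is 0.72 counting all enrolled and 0.87 counting dosed women. With the Study Summary's 25 women, one undosed woman is enough to move the count: 6 of 25 against 5 of 24, with chances 0.77 and 0.89.

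**3. The 72-hour set.** Planned attrition before 48 hours is 24 − 20 = 4 women. Suppose these 4 leave the set and there are 5 cases in all. Counting everyone gives 5/24 = 20.8%. The 72-hour set gives 5/20 = 25% if none of the cases was among the 4, and 1/20 = 5% if four were.

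**4. How short exposure may be.** Section 1.1 reports that "75% of women with sFlt-1/PlGF >0.85 deliver within one week and 85% within two weeks", against 10% and 15% with a lower ratio. If a share e of enrolled women has a ratio above 0.85, delivery within a week is 0.75e + 0.10(1 − e):
- e = 0.5: 0.375 + 0.05 = 42.5%
- e = 0.9: 0.675 + 0.01 = 68.5%
- a majority needs e above (0.50 − 0.10)/0.65 = 61.5%

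The share e is an assumption. The roughly 90% in 1.1 refers to elevated sFlt-1, not to the ratio. Entry also requires that delivery is not expected within 48 hours, which would lower these figures.

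**5. Possible effect of short exposure (illustration only).** Assume a constant hazard with a 14-day risk of 20%, and deliveries spread evenly within each week. Average risk is then 5.38% for women delivering in week 1, 15.36% in week 2, and 20% for those reaching day 14.
- 68.5%, 9.5% and 22% in these groups: 0.685 × 5.38 + 0.095 × 15.36 + 0.22 × 20 = 9.5%
- 20%, 30% and 50%: 0.20 × 5.38 + 0.30 × 15.36 + 0.50 × 20 = 15.7%

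Neither the hazard nor the 14-day period comes from the documents.

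**The case against.** **The 72-hour set may not be meant for safety.** Section 4.4.2 ties it to the primary outcome, so it may apply to blood pressure only. That is a reasonable reading, but the section does not say so, and 7.2 is written without exception. If it is right, the undosed women return to the liver denominator.

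**Few women may go undosed.** Section 3.1 says that women expected to remain undelivered for 48 hours will receive drug, and step 2 shows little effect for 1 to 4 of 24. This stands, and it is why the effect is called modest.

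**Other safeguards do not depend on 7.2.** The FDA is notified after one case of liver toxicity (section 8), and the DSMB reviews after every 6 enrolled subjects (8.6). This also stands. The point concerns the reported proportion and the 20% rule.

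**Risk over treatment as actually used is a legitimate target.** If the 20% describes similar women followed to delivery, a crude proportion is a like-for-like comparison. This cannot be dismissed, because the plan gives the 20% no time period. That is a reason to state one.

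A reader might also infer that planned attrition alone moves the result across 20%: 4/24 = 16.7% against 4/19 = 21.1%. The documents do not support this. The attrition in 7.1 is delivery before 48 hours of treatment, so these are not never-dosed women, and some may have had a liver test. The plan's own retained number is 20, and 4/20 = 20.0% does not exceed 20%.

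**Conclusion.** The concern holds in a limited form. Section 7.2 puts women who cannot have the event into the denominator, 4.4.1 does the same for the stopping rule, and 4.4.2 contradicts 7.2 with a set that could lose early toxicity. The direction of bias under 7.2 is certain. Its size from undosed women is modest: a true 20% shows as 15.8% at worst over the assumed range, and the case count needed at 24 women changes only with 5 undosed. With 25 women it changes by one case as soon as one woman is undosed.

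Three stronger readings go beyond the documents:
- **Most women will be on drug for under a week.** This requires more than 61.5% of enrolled women to have a high ratio, and no section gives that share.
- **Short exposure pulls the proportion well below 20%.** The figures in step 5 rest on an assumed hazard and an assumed time period. Dilution by short exposure is possible but not shown.
- **A result below 20% would be taken as showing that dosing to 34 weeks is safe.** No section makes that a success criterion. Section 2 speaks only of further evaluating safety.

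**What to change.** 1. For liver toxicity and side effects, define the safety set as all preeclamptic women who took at least one dose, with no 72-hour minimum. Naming the preeclamptic women also settles that the 12 healthy women are not part of the 7.2 denominator.
2. Reconcile 4.4.2 with 7.2, and say which analyses, if any, use the 72-hour set.
3. Report how many dosed women had no liver test after the first dose, and give the liver proportion also among those with at least one.
4. In 7.1, 4.4.1 and 8.4, state which denominator and which time period the 20% refers to.
5. Add a summary of time on drug and the cumulative incidence of liver toxicity by days 2, 7 and 14, with numbers still on drug and delivery as a competing event.
6. Reconcile the treatment durations (4.4.1 against 5.2 and 8.4) and the liver-test intervals (3.1 and 6.2 against 5.5), since both determine the exposure and ascertainment behind the proportion.

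The cost is SAP wording and one table. Dose, test and delivery dates should be available from pharmacy records and the planned chart abstraction. The reported percentage will be slightly higher and less precise.

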8.1 Definitions

Unanticipated Problems Involving Risk to Subjects or Others

Any incident, experience, or outcome that meets all of the following criteria:

- Unexpected in nature, severity, or frequency (i.e. not described in study-related documents such as the IRB-approved protocol or consent form, the investigators brochure, etc)
- Related or possibly related to participation in the research (i.e. possibly related means there is a reasonable possibility that the incident experience, or outcome may have been caused by the procedures involved in the research,

Adverse Event

An **adverse event** (AE) is any symptom, sign, illness or experience that develops or worsens in severity during the course of the study. Intercurrent illnesses or injuries should be regarded as adverse events. Abnormal results of diagnostic procedures are considered to be adverse events if the abnormality:

- results in study withdrawal
- is associated with a serious adverse event
- is associated with clinical signs or symptoms
- leads to additional treatment or to further diagnostic tests
- is considered by the investigator to be of clinical significance

Adverse Event Grading

Adverse events will be graded using the Common Terminology for Criteria for Adverse Events (CTCAE) version 4.03 (published June 14, 2010).

Grade 1: Mild; asymptomatic or mild symptoms; clinical or diagnostic observations only; intervention not indicated; limiting. (e.g., GI distress, nausea, vomiting; flushing)

Grade 2: Moderate; minimal, local or noninvasive intervention indicated. (e.g. GI distress requiring IV therapy)

Grade 3: Severe or medically significant but no immediately life-threatening; hospitalization or prolongation of hospitalization indicated; disabling.

Grade 4: Life-threatening consequences; urgent intervention indicated.

Grade 5: Death related to AE.

Adverse Event Reporting Period

The study period during which adverse events must be reported is defined as the period from the initiation of any study procedures to the end of the study treatment follow-up. For this study, the study treatment follow-up for the mother is defined as until discharge from the hospital and the infant as until discharge or 30 days of life, whichever occurs first.

Preexisting Condition

A preexisting condition is one that is present at the start of the study. A preexisting condition will be recorded as an adverse event if the frequency, intensity, or the character of the condition worsens during the study period.

General Physical Examination Findings

At screening, any clinically significant abnormality will be recorded as a preexisting condition. At the end of the study, any new clinically significant findings/abnormalities that meet the definition of an adverse event will also be recorded and documented as an adverse event.

Post-study Adverse Event

The investigator will follow all unresolved adverse events until the events are resolved, the subject is lost to follow-up, or the adverse event is otherwise explained. At the last scheduled visit, the investigator will instruct each subject to report any subsequent event(s) that the subject, or the subject's personal physician, believes might reasonably be related to participation in this study. The investigator will notify the IRB of any death or adverse event occurring at any time after a subject has discontinued or terminated study participation that may reasonably be related to this study. The IRB will also be notified if the investigator becomes aware of the development of cancer or of a congenital anomaly in a subsequently conceived offspring of a subject that has participated in this study.

Abnormal Laboratory Values

A clinical laboratory abnormality will be documented as an adverse event if any one of the following conditions is met:

- The laboratory abnormality is not otherwise refuted by a repeat test to confirm the abnormality
- The abnormality suggests a disease and/or organ toxicity
- The abnormality is of a degree that requires active management; e.g. discontinuation of the study agent, more frequent follow-up assessments, further diagnostic investigation, etc.

Hospitalization, Prolonged Hospitalization or Surgery

Any adverse event that results in hospitalization or prolonged hospitalization will be documented and reported as a serious adverse event unless specifically instructed otherwise in this protocol. Any condition responsible for surgery will be documented as an adverse event if the condition meets the criteria for an adverse event.

Neither the condition, hospitalization, prolonged hospitalization, nor surgery are reported as an adverse event in the following circumstances:

- Hospitalization or prolonged hospitalization for diagnostic or elective surgical procedures for a preexisting condition. Surgery should **not** be reported as an outcome of an adverse event if the purpose of the surgery was elective or diagnostic and the outcome was uneventful.
- Hospitalization or prolonged hospitalization required for an efficacy measurement for the study.
- Hospitalization or prolonged hospitalization for therapy of the target disease of the study, unless it is a worsening or increase in frequency of hospital admissions as judged by the clinical investigator.
- Surgery is undertaken for delivery of the infant (cesarean section).

Potential Risks and/or Toxicities of Study Agent

The most serious risk of vitamin B₃-amide is liver toxicity. Potential risks of vitamin B₃-amide at doses \leq 3 gm/day include:

Rare (< 1%)

Liver toxicity
Facial erythema
Hives
Sore mouth
Dry hair
Fatigue

Infrequent (1-10%)

Flushing (< 2%)
Headache (1%)
Nausea (< 2%)
Heartburn (< 2%)

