8.2 Recording of Adverse Events

At each contact with the subject, the investigator will seek information on adverse events by specific questioning and, as appropriate, by examination. Information on all adverse events will be recorded immediately in the source document, and also in the appropriate adverse event module of the case report form (CRF). All clearly related signs, symptoms, and abnormal diagnostic procedures results will be recorded in the source document, grouped under one diagnosis.

All adverse events occurring during the study period will be recorded. The clinical course of each event will be followed until resolution, stabilization, or until it has been determined that the study treatment or participation is not the cause. Serious adverse events that are still ongoing at the end of the study period will be followed up to determine the final outcome. Any serious adverse event that occurs after the study period and is considered to be possibly related to the study treatment or study participation will be recorded and reported immediately.

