8.4 Stopping Rules

The study will be stopped under the following circumstances:

- Any maternal or fetal death deemed to be related or possibly related to study participation
- >20% subjects experience liver toxicity (defined as AST or ALT \geq 3x ULN within 24 hours of study drug)

Specific rules to stop study intervention for individual subject

- Delivery, or 34 weeks, which ever occurs first
- Liver toxicity (LFTs \geq 3x ULN within 24 hours of study drug)
- Maternal side effects that cannot be managed with oral medication

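### Section 8.1 contradicts itself on whether the condition leading to a cesarean is reported as an adverse event, so AE/SAE capture can depend on mode of delivery

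*Combined protocol and SAP*

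**What the plan says.** Three statements in Section 8.1, under the subheading on hospitalization and surgery, bear on the point.

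- The general rule for surgery: "Any condition responsible for surgery will be documented as an adverse event if the condition meets the criteria for an adverse event".
- The lead-in to the exemption list, which follows directly: "Neither the condition, hospitalization, prolonged hospitalization, nor surgery are reported as an adverse event in the following circumstances".
- The last of the four listed circumstances, which carries no qualification: "Surgery is undertaken for delivery of the infant (cesarean section".

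The third circumstance, hospitalization for therapy of the target disease, does carry a qualification. It applies "unless it is a worsening or increase in frequency of hospital admissions as judged by the clinical investigator".

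The same subsection makes an AE that leads to or prolongs hospitalization a serious AE "unless specifically instructed otherwise in this protocol". Section 8.2 adds, without exception, "All adverse events occurring during the study period will be recorded".

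**The concern.** The lead-in exempts the condition along with the procedure and the hospital stay. For elective surgery on a preexisting problem that is harmless, because the condition was there before the study. For a cesarean in early-onset preeclampsia it is not, because the condition that prompts delivery may be a new complication that arose on study drug. The background (Section 1.1) says the disease resolves only with delivery, so worsening will often end in delivery, and some of those deliveries will be cesarean.

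At stake is whether serious maternal complications are entered, graded, assessed for causality and counted in the same way for every woman. The medical monitoring in Section 8.5 rests on the number and type of serious AEs. The preeclampsia cohort has no untreated comparison group, so a loss of events tied to mode of delivery could not be seen or corrected by comparing arms.

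**Working it through.** No arithmetic applies: the plan states no figure on this point, and the documents give no cesarean or complication rate. The check is textual.

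**Step 1. Does the list reach the condition?** Yes. The lead-in names the condition first, then the hospital stay and the surgery, and applies to every item. The cesarean item has no exception for worsening, emergency or fetal indication.

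**Step 2. Does the worsening exception rescue it?** Not on the wording. That exception sits inside the target-disease item and limits only that item. A woman whose disease worsens and who is delivered by cesarean falls outside the third circumstance but still inside the fourth.

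**Step 3. Does anything set an order of precedence?** No. The sentence on conditions responsible for surgery and the list stand next to each other and give opposite instructions. The serious-AE rule yields to specific instructions elsewhere in the protocol, which leans toward the list. Section 8.2 does not settle it, because the question is whether the condition is to be handled as an AE at all.

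**Step 4. One case followed through.** Take eclampsia on day 5 of study drug.

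| | Vaginal delivery | Cesarean, list read literally |
|---|---|---|
| Meets the 8.1 AE definition (new or worsening illness) | Yes | Yes |
| Covered by a listed circumstance | No, if judged a worsening of the target disease | Yes, the cesarean item |
| Result | AE, and serious if hospitalization is prolonged | Not reported as an AE |

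**Step 5. Which events have another route, whatever the mode of delivery?**

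- Death: the stopping rule covers "Any maternal or fetal death deemed to be related or possibly related to study participation" (Sections 4.4.1 and 8.4).
- Liver toxicity and early delivery: the opening of Section 8 says "The FDA will be notified after 1 case of liver toxicity and after every 1 case of delivery within 48 hours of enrollment". Section 8.6 adds DSMB notices after every 2 cases of each, counting early delivery from the start of nicotinamide. Liver toxicity also has stopping rules (4.4.1, 8.4) and a planned analysis (7.1).
- Delivery for fetal reasons, including umbilical artery Doppler changes: a stopping rule in 4.4.1, not repeated in 8.4.
- Part of the rest: the safety-endpoint table in 3.2 has rows for hematocrit fall with bleeding (some abruptions) and liver enzymes (part of HELLP). Low platelets may enter through the separate rule in 8.1 on abnormal laboratory values.

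**Step 6. What is left?** Eclampsia and pulmonary edema have no row in the 3.2 table. Neither triggers a prompt notice when delivery falls after 48 hours. Abruption is covered only in part. Section 7.1 plans descriptive reports of side effects and fetal effects but no analysis of maternal complications as such. For these events the AE/SAE record is the main route, and the list can close it.

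**The case against.** The strongest reply is that a sensible reader would take the cesarean item to exempt only the surgery it names. The preceding sentence, the rule that a preexisting condition is recorded if it worsens, and the duty in Section 8.2 to record all AEs all point that way. Information would reach the file in any case: charts are abstracted for delivery and neonatal data, the 30-day calls ask about adverse events, and the DSMB reviews data after every 6 subjects. For expedited reporting, Section 8.3.1 is framed around study events that are unexpected and associated with the agent, and an unanticipated problem in 8.1 can be any incident. A complication judged expected or unrelated would fall outside the Section 8.3 minimum after vaginal delivery too.

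Much of this stands. It limits the harm mainly to AE/SAE entry, grading and tabulation, and to the serious-AE review in Section 8.5; the whole reporting chain does not fail. It does not remove the contradiction. The milder reading requires the reader to ignore the word naming the condition in the lead-in. Chart abstraction alone does not produce a grade, a causality judgment or a reporting clock.

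A reader might also infer that the most serious maternal and fetal events as a class go unreported, or that the trial's safety objective is biased toward a finding of safety. The documents do not support either. The routes in step 5 cover several of the gravest events. Objective 2 in the Study Summary defines safety by liver enzymes, which do not pass through this list, and Section 8.1 names liver toxicity as the agent's most serious risk.

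**Conclusion.** The point holds as an internal contradiction in the AE rules with a definite direction. Two adjacent instructions conflict, and the one that reads as the specific rule drops a condition from AE/SAE reporting because the woman was delivered by cesarean. The events exposed are mainly serious maternal complications, such as eclampsia, pulmonary edema and abruption, arising more than 48 hours after enrollment. The primary MAP outcome, the liver-enzyme endpoint and the stopping rules are untouched.

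The size cannot be given as a number. It would need the number of such complications, the share delivered by cesarean, and how often staff apply the list literally, and the documents supply none of these. A count built on an assumed cesarean share would measure the assumption. The conclusion assumes only that some staff will follow the list as written, which the wording permits.

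**What to change.** Reconcile the passages in Section 8.1. Limit the cesarean item to the operation and its hospital stay, and take the condition out of the lead-in as far as that item is concerned. Wording along these lines would do: *Cesarean section is not in itself an adverse event; the maternal or fetal condition that led to it is recorded, graded and reported if it meets the AE or SAE criteria.* The list would then agree with the sentence before it and with Section 8.2.

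The cost is one sentence of amended text, a few more AE records taken from charts that are already abstracted, and a somewhat higher reported AE count. Clinical care does not change.
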